8.1 Efficacy Assessments

8.1.1 Assessment of OCS Dose

All participants who meet eligibility criteria and enter the study will receive open-label

tezepelumab during the induction phase (Week 0 to Week 4). During this phase, participants should remain stable on their baseline (Week 0) OCS dose.

During the OCS reduction and maintenance phase, participants will reduce their OCS dose until the participant discontinues OCS or reaches the lowest OCS dose possible. OCS dose reduction may be slowed down in case of a first test result indicating complete AI, an elevated ACQ-6 score, or a first asthma exacerbation. OCS dose reduction will be stopped for the duration of the trial in case of a second test result confirming complete AI or a second asthma exacerbation (details provided in Section 8.1.2, Appendix M, and the schedule provided in Table 7).

No further reductions will be made to OCS dose from Week 48 onwards.

In case of exacerbations, participants will be managed as per details provided in Section 6.5.1.1. Additionally, in case the participant experiences asthma deterioration or an exacerbation, increase in the maintenance OCS daily dose is permitted per investigator discretion. Once the participant recovers from the first asthma exacerbation, further OCS dose reductions will be allowed at a slower pace during the reduction and maintenance phase as described in Table 8. No reductions are allowed after a second exacerbation.

All OCS dose changes, including temporary or permanent interruption of OCS reduction, will be documented in the source documentation and recorded in the appropriate eCRF form, along with reason for change.

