^a Partial AI cortisol testing confirmed with ACTH stimulation testing or the alternative method described in Appendix M. After repetition of the test 2 months later, the decision to further reduce OCS dose will be based on the morning cortisol test results. If test results are normal, the OCS dose may be reduced directly to 0 mg/day (if participant is receiving

^{≤3} mg); the participant will continue receiving 1 mg Q4W if still at risk. If complete AI is indicated, OCS dose will not be modified.
b If morning cortisol test results again indicate complete AI at 3 months, the OCS dose will not be modified as this is the final attempt. If morning cortisol test results indicate risk AI, then reductions will be 1 mg Q4W and, if normal, then reductions will be 2.5 mg Q4W.

Rescue OCS Down-titration After Recovery From the First Event of an Asthma Exacerbation or Deterioration Table 8

Initial OCS dose/day	Rescue OCS down-titration af	ter recovery from an asthma exacerbation	after recovery from an asthma exacerbation or deterioration to reach an OCS dose of:
	10 mg	5 mg	0 mg
> 20 mg	Reduction of 5 mg of the daily dose Q4W until reaching a dose of 10 mg/day	Reduction of 2.5 mg of the daily dose Q4W until reaching a dose of 5 mg/day	No AI: Reduction of 2.5 mg of the daily dose Q4W Partial AI: 1 mg/day of the daily dose Q4W and repeat test 2 months later ^a Complete AI: No OCS dose reduction and repeat test 3 months later ^b
> 10 mg to ≤ 20 mg	Reduction of 5 mg of the daily dose Q4W until reaching a dose of 10 mg/day	Reduction of 2.5 mg of the daily dose Q4W until reaching a dose of 5 mg/day	No AI: Reduction of 2.5 mg of the daily dose Q4W Partial AI: 1 mg/day of the daily dose Q4W and repeat test 2 months later ^a Complete AI: No OCS dose reduction and repeat test 3 months later ^b
> 5 mg to ≤ 10 mg		Reduction of 2.5 mg of the daily dose Q4W until reaching a dose of 5 mg/day	No AI: Reduction of 2.5 mg of the daily dose Q4W Partial AI: 1 mg/day of the daily dose Q4W and repeat test 2 months later ^a Complete AI: No OCS dose reduction and repeat test 3 months later ^b
S mg			No AI: Reduction of 2.5 mg of the daily dose Q4W Partial AI: 1 mg/day of the daily dose Q4W and repeat test 2 months later ^a Complete AI: No OCS dose reduction and repeat test 3 months later ^b

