8.2.1 Hypothalamic-pituitary-adrenal Axis Evaluation

For all participants, HPA axis integrity will be evaluated after 4 weeks on 5 mg/day and prior to tapering down the OCS dose (for participants with baseline OCS doses equal to 5 mg/day, this will be assessed 4 weeks after the first dose of tezepelumab administration and before initiation of the OCS reduction phase).

First, a screening method with morning serum cortisol is done (8-9 am morning cortisol level), to evaluate whether the participant has:

- Normal cortisol levels (Table 9)
- Complete AI (Table 9).

Cortisol levels from the morning cortisol test that are below normal range and above the complete AI range are considered 'indeterminate' (Table 9), and require additional testing described below (for sites where tetracosactide is not available or not registered, please see Appendix M).

If the morning cortisol is in the indeterminate range, then the ACTH stimulation test is done within approximately 1 week (see Section 8.2.1.2 for details). The ACTH stimulation test is more specific than the morning cortisol test, and can determine whether the participant has:

- Normal cortisol levels: > 450 nmol/L (> 675 nmol/L for participants taking oestrogen-containing contraceptives)
- Complete AI: < 250 nmol/L (< 375 nmol/L for participants taking oestrogen-containing contraceptives)
- Partial AI: 250 to 450 nmol/L (375 to 675 nmol/L for participants taking oestrogen-containing contraceptives).

For morning serum cortisol and ACTH stimulation tests, hold OCS dose and other concomitant medications that could interfere with cortisol results as follows (see Section 6.5):

- The last OCS dose should be taken \geq 24 hours prior to testing
- Participants must not take ICS (or ICS/LABA if in single inhaler) treatment on the
 morning of the morning cortisol level/ACTH stimulation test (for participants taking a
 once-daily ICS/LABA formulation, eg, fluticasone furoate/vilanterol, participants must
 not take the treatment ≤ 24 hours prior to the morning of the morning cortisol
 level/ACTH stimulation test)
- If a participant requires a short course of macrolides, antivirals, or azoles, there must be a window of ≥ 1 week prior to the testing of cortisol levels.

The process will be as described in Figure 3.

[figure not shown]

Figure 3 Hypothalamic-pituitary-adrenal Axis Evaluation

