Figure 3: For normal cortisol levels with concurrent signs/symptoms of AI, OCS down-titration should continue at a slower pace (1 mg Q4W). For complete AI identified via morning cortisol testing, refer to Section 8.2.1.1 for instructions on 3-month repeat testing. For partial AI or complete AI identified via ACTH stimulation test see Section 8.2.1.2 for instructions on 2-month or 3-month repeat testing respectively.

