8.2.1.1 Morning Cortisol Test

The morning cortisol test will be done in all participants 4 weeks after reaching the 5 mg dose of OCS, and before further dose reductions. It is also done 3 months after a participant has completed a test indicating complete AI.

Serum samples for cortisol will be collected between 8 and 9 am and will be sent to a central laboratory for evaluation.

The following values will be used to define AI status for the morning cortisol test:

Table 9 Cortisol Status

AI status	SI units	Participants taking oestrogen- containing contraceptives
Normal	>350 nmol/L	>700 nmol/L
Indeterminate results	100 - 350 nmol/L	200 - 700 nmol/L
Complete AI	<100 nmol/L	<200 nmol/L

Once the results are available, the site will inform the participant of the results via telephone. For sites where tetracosactides are available, and depending on the result, the actions that will be implemented are as follows:

- If cortisol levels are within normal range and the participant does not exhibit any signs and/or symptoms of AI, the participant will continue OCS down-titration by 2.5 mg Q4W
- If cortisol levels are within normal range but the participant exhibits signs and/or symptoms of AI, then OCS down-titration should continue at a slower pace (1 mg Q4W).
- If cortisol levels are below the normal range and above the complete AI range (indeterminate result), then the participant will be instructed to maintain the current OCS dose and come back to the site within 1 week for an ACTH stimulation test (Section 8.2.1.2)
- If complete AI is confirmed, sites will inform participant that the OCS dose will remain the same without further reduction until there is evidence of recovery from the complete AI without worsening of asthma control. The morning cortisol test and associated clinical assessments (see Table 1) will be repeated 3 months later. After the repeat morning cortisol test, the site will inform the participant based on the results as follows:
 - If morning cortisol results indicate normal cortisol values, then reductions will be 2.5 mg Q4W, and the participant would subsequently move to maintenance at the OCS lowest possible dose
 - If morning cortisol results are indeterminate, then reductions will be delayed further, and the participant would return approximately 1 week later for an ACTH stimulation test:
 - o If normal result after ACTH stimulation (Table 10): reduce by 2.5 mg Q4W then move to maintenance at the lowest possible dose

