 - If the result is partial AI after ACTH stimulation (Table 10): reduce by 1 mg Q4W then move to maintenance at the lowest possible dose
 - If complete AI result after ACTH stimulation (Table 10): OCS dose will not be reduced further, and participant will continue at the current OCS dose.
 - If morning cortisol tests again indicate complete AI at 3 months, the OCS dose will not be modified as this is the final attempt. The participant would move to maintenance at the current OCS dose.

For sites where tetracosactide is not available or not registered, please see Appendix M.

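### Footnote b of Tables 7 and 8 starts a 1 mg Q4W taper on an undefined 'risk AI' repeat cortisol, where Section 8.2.1.1 holds the dose for an ACTH test

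*Protocol*

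**What the plan says.** Protocol Section 8.1.2 makes Table 7 the titration schedule; Table 8 applies after recovery from a first asthma event. Both tables hold the dose when complete AI is found and call for a repeat test at 3 months. Footnote b then gives three outcomes for the repeat morning cortisol. Complete AI again means no change, as the last attempt. A normal result means 2.5 mg Q4W. For the outcome in between: "If morning cortisol test results indicate risk AI, then reductions will be 1 mg Q4W". No further test is mentioned. 'Risk AI' is not a category in Table 9, Table 10 or Appendix M.

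The note under Figure 3 sends one group elsewhere: "For complete AI identified via morning cortisol testing, refer to Section 8.2.1.1 for instructions on 3-month repeat testing". Section 8.2.1.1 says of that repeat: "If morning cortisol results are indeterminate, then reductions will be delayed further", with an ACTH test about a week later. A normal ACTH result gives 2.5 mg Q4W. The other two branches read "If the result is partial AI after ACTH stimulation (Table 10): reduce by 1 mg Q4W then move to maintenance" and "If complete AI result after ACTH stimulation (Table 10): OCS dose will not be reduced further".

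The other group is covered by "For partial AI or complete AI identified via ACTH stimulation test see Section 8.2.1.2". That section refers on to Figure 3, which is not visible in the text available for this review. The general rule in Section 8.2.1 is "If the morning cortisol is in the indeterminate range, then the ACTH stimulation test is done within approximately 1 week". Sites without tetracosactide use Appendix M, which asks for a fourth sample about a week after a third result of 100 to 350 nmol/L.

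**The concern.** The participants concerned have already shown complete AI on 5 mg/day, roughly a physiological dose. Whether they go below it is a safety decision, and the protocol treats the ACTH test as the more specific of the two tests. Two pieces of current text give different instructions for one result, and nothing says which prevails.

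Section 8.1.1 adds to the difficulty. It says "OCS dose reduction will be stopped for the duration of the trial in case of a second test result confirming complete AI", and points to Table 7 among the places for detail. When the repeat is indeterminate, footnote b leaves out the very test that could supply that second result.

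The final prescribed dose also feeds the primary endpoint of discontinuing OCS and the secondary endpoint of a reduction of at least 50%. In a single-arm study nothing cancels such differences.

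**Working it through.** The plan gives no figure to reproduce, so the main check sets the texts side by side.

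**Step 1: what 'risk AI' can mean.** Table 9 gives three morning cortisol bands: above 350, 100 to 350, and below 100 nmol/L (above 700, 200 to 700 and below 200 with oestrogen-containing contraceptives). Footnote b also has three outcomes and bases them on the morning cortisol. Matching the two makes 'risk AI' the indeterminate band. A single morning cortisol cannot give partial AI under Table 9.

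**Step 2: one result under each rule.** Take a 3-month repeat of 200 nmol/L, no oestrogen.

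| Text | Immediate action | Then |
|---|---|---|
| Footnote b | Start 1 mg Q4W | No further test named |
| Section 8.2.1.1 | Hold, ACTH in about 1 week | Normal 2.5 mg Q4W; partial 1 mg Q4W; complete no reduction |
| Appendix M, third and fourth tests | Second sample in about 1 week | Both below 250: delay titration; one at or above 250 but the fourth not above 350: 1 mg Q4W; fourth above 350: 2.5 mg Q4W, or 1 mg Q4W with symptoms |

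The resulting rates agree if the confirmatory result is partial AI. They differ most if it is complete AI.

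**Step 3: how firm the conflict is in each branch.**
- Complete AI found by morning cortisol: explicit, because Section 8.2.1.1 addresses this exact repeat.
- Complete AI found by ACTH: inferred from the general rules (Section 1.3 footnote e, Sections 4.1, 8.2.1 and 8.2.1.2).
- Appendix M sites: the second sample is required. The hold during that week is only implied in the appendix, but Section 4.1 states it for an indeterminate result.

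**Step 4: which endpoints can move.** Illustration only, with assumptions: no interruption for asthma, 3 months taken as 13 weeks, result acted on at once.

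*Baseline 5 mg.* First test Week 4, repeat Week 4 + 13 = 17.
- Confirmatory test would show complete AI. Section 8.2.1.1 holds 5 mg. Under footnote b with no later test stopping the taper, the steps fall at Weeks 17, 21, 25, 29 and 33, so the dose is 0 mg from Week 33 and the participant counts as discontinued at Week 52.
- Confirmatory test would be normal. Section 8.2.1.1 steps at Weeks 18 and 22, giving 0 mg from Week 22. Under footnote b the Week 28 dose is 5 − 3 = 2 mg, so here the footnote counts against discontinuation. A normal retest at Week 25 would allow 0 mg directly and remove the difference.

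Both 0 mg doses meet the rule for final dose of at least 2 weeks without change: Week 22 is 6 weeks before Week 28, and Week 33 is 19 weeks before Week 52.

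*With a 2-month retest.* Elsewhere 1 mg Q4W is paired with a retest at 2 months; footnote b does not mention one. If done at 8 weeks, the participant has spent 4 weeks on 4 mg and 4 on 3 mg. A complete-AI result then holds 3 mg. At baseline 7.5 mg, 3 mg is (7.5 − 3)/7.5 = 60% reduction, against (7.5 − 5)/7.5 = 33.3% at 5 mg. The 50% threshold is met at 3 mg from baseline 6 mg and at 5 mg only from baseline 10 mg, so baselines from 6 to below 10 mg change status.

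*5 mg/day or less.* Every path starts at 5 mg and none of these rules raises the dose.

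*Scale.* Each participant reclassified moves a proportion by 1/300 = 0.33 percentage points.

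**The case against.** The best defence is that footnote b is shorthand for the end states of Section 8.2.1.1: complete, partial and normal lead to no change, 1 mg and 2.5 mg in both. Footnote a in the same tables ties partial AI to confirmation by ACTH or Appendix M and speaks of those participants as still at risk. On that reading the doses match and only a step is missing. The confirmatory test is also stated in several other sections, and Section 8.1.2 refers to Section 8.2.1 for detail. The footnote's taper is the slowest in the protocol. Participants with AI are taught to recognise symptoms and use emergency cards, and adrenal crisis is an event of special interest with its own guidance.

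Much of this stands. The alternative reading is possible, the explicit conflict is confined to one branch, and the safeguards are real. It does not dispose of the point. Footnote b rests on the morning cortisol, omits the confirmation that footnote a names, and sits in the table that sites are told to follow.

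A reader might also infer that Table 8 has no rule for complete AI at the 2-month repeat, because its footnote a lacks a sentence found in Table 7. Table 8's own cells already bar reduction for complete AI, so this is only tidying.

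**Conclusion.** The concern holds as a conflicting dosing instruction. It is explicit where complete AI was found by morning cortisol, and an inconsistency with the general rules or Appendix M otherwise. It rests on reading 'risk AI' as indeterminate; on the other reading, a required test is still missing from the table and a term undefined.

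A reader might infer that the protocol directs tapering in confirmed complete AI. It does not: every text, including footnote b, holds the dose on such a result. The risk is that the confirmatory test is skipped. A reader might also infer a known bias in the primary results. The documents give no frequency for complete AI followed by an indeterminate repeat, the effect on discontinuation can go either way, and a later retest can remove it. The week-by-week figures show only that a change is possible. It deserves correction because the consequence is one of safety and the remedy is nearly free.

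**What to change.** In footnote b of Tables 7 and 8, replace the 'risk AI' clause with: if the repeat morning cortisol is indeterminate (Table 9), keep the dose unchanged, do the ACTH stimulation test (or the Appendix M second sample), and then follow Section 8.2.1.1 (or Appendix M). Leave the rules for normal and complete AI as they are.

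Do not restrict 1 mg Q4W to confirmed partial AI. Sections 8.1.2 and 8.2.1.2 and the fourth test in Appendix M also use that pace for symptoms, so the restriction would create a new contradiction.

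Send sites a short reminder. Copying Table 7's complete-AI sentence into Table 8 footnote a is optional. The cost is one clause in each of two tables and a site communication; both confirmatory tests are already required.

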8.1.3 Assessment of Asthma Exacerbation

During the study, an asthma exacerbation will be defined as a worsening of asthma symptoms that leads to any of the following:

- A temporary bolus/burst of systemic corticosteroids (or a temporary increase in stable OCS background dose) for at least 3 consecutive days to treat symptoms of asthma worsening; a single depo-injectable dose of corticosteroids will be considered equivalent to a 3-day bolus/burst of systemic corticosteroids.
- An ER or urgent care visit (defined as evaluation and treatment for < 24 hours in an emergency department or urgent care centre) due to asthma that required systemic corticosteroids (as per the above).
- Inpatient hospitalisation (defined as admission to an inpatient facility and/or evaluation and treatment in a healthcare facility for ≥ 24 hours) due to asthma.

Note: Participants who experience an exacerbation during the screening period (between Visits 1 and 2) can be granted an extension of the screening period to ensure that the participant recovers from an asthma exacerbation and the OCS dose is stabilised.

The investigator must justify the decision for defining an event of worsening asthma as an exacerbation and record it in the source documents and eCRF.

The participant may remain in the study after an exacerbation and continue to receive study drug if the investigator judges that it is medically appropriate for the participant to do so and will be managed as per the details provided in Section 6.5.1.1.

Reasonable attempts should be made by the investigator to bring the participant into the study site for patient-initiated therapy for asthma worsening, particularly when it results in additional treatment being prescribed. Study site evaluations for asthma worsening may occur as an unscheduled visit or as part of a routine centre visit if the worsening happens to occur in line with a scheduled visit. A copy of the medical record should be obtained for exacerbations evaluated and treated at non-study sites (eg, by the primary care provider or at an emergency department/hospital). Details should be entered into the exacerbation eCRF in a timely fashion. Changes in concomitant medications due to exacerbations must be recorded in the appropriate module of the eCRF.

8.1.4 Spirometry

General requirements

Lung function (FEV₁) will be measured post-BD at the study site by spirometry using equipment provided by a central vendor. The central spirometry vendor will ensure that the spirometer meets American Thoracic Society/European Respiratory Society (ATS/ERS) recommendations and that the study site personnel who will be performing the testing are properly certified.

Spirometry will be performed by the investigator, or designee, according to ATS/ERS guidelines (Graham et al, 2019).

Spirometry calibration and data quality checks (including monitoring of unexpectedly high variability of results) will be detailed in a separate spirometry procedures manual and in the monitoring plan.

- Participants should avoid engaging in strenuous exertion for at least 30 minutes prior to all lung function assessments at the study site.
- Participants should avoid eating a large meal for at least 2 hours prior to all lung function assessments at the study site.

Time of day for scheduled site visit spirometry

Spirometry testing should be done according to the SoA (Table 1). It is recommended that all spirometry assessments are performed within \pm 2 hours of the time of day that the Visit 2 spirometry is performed, if possible.

Post-BD spirometry technique

Post-BD spirometry procedures will be performed according to the SoA. Bronchodilation can be induced using albuterol (90 μ g metered dose) or salbutamol (100 μ g metered dose) up to a maximum of 4 inhalations. In rare cases where a participant has an adverse or allergic reaction to albuterol/salbutamol, levalbuterol (45- μ g metered dose; up to a maximum of 4 inhalations) can be used. Levalbuterol will not be supplied by the sponsor. It is highly recommended to use a spacer device for this procedure.

Nebulizer should not be used. A lower total dose (eg, 2 inhalations instead of 4 puffs) can be used if there is a concern about any effect on the participant's heart rate, tremor or safety; the reason should be noted in the participant's medical record.

Further details on spirometry are provided in the spirometry manual.

Record keeping

A signed and dated copy of the spirometry printout must be kept at the study site for source

data verification. The printout must be marked with the study code, enrolment code, date and time of measurement, and visit number.

Date and time (and result) of the spirometry data will be transcribed from source data into the electronic database.

8.1.5 Patient-reported Outcomes (PRO)

Patient-reported outcomes (PRO) data will be captured electronically at home using a handheld device (ePRO). The ePRO device is the only acceptable source; data from paper questionnaires are not acceptable. Site personnel will be trained on using the ePRO. Detailed procedures for using the ePRO and training the participants will be described in a separate instruction manual. Participants will be trained on at-home use of the ePRO at Visit 2. Training will include explanation of device functionality and its proper use. Participants will also be asked to verify completion of training on the ePRO. Participants will be asked to bring the device back at each study visit. Data for all PROs will be collected in accordance with Table 1. Participants should be informed that the recording made electronically cannot be retrospectively or prospectively entered and must be completed within a defined time window (\pm 2 days; this defined window may or may not coincide with the on-site visit). Participants will also be provided with information about when and where to request help if problems occur. The investigator/authorised delegate will check the participant's adherence to completing the ePRO as described in Table 1. There will be triggers in the PROs to alert investigators to signs of worsening of asthma and advising them to contact the participant for evaluation. Compliance alerts will remind participants to complete their assessments and notify investigators of poor compliance. These alerts will be described in a separate guide.

8.1.5.1 Asthma Control Questionnaire 6

The ACQ-6 is a shortened version of the ACQ that assesses asthma symptoms (night time waking, symptoms on waking, activity limitation, shortness of breath, wheezing, and use of short-acting β2 agonists), omitting the FEV₁ measurement from the original ACQ score.

Participants will be asked to recall how their asthma has been during the previous week by responding to 1 BD use question and 5 symptom questions.

Questions are weighted equally and scored from 0 (totally controlled) to 6 (severely uncontrolled). The mean ACQ-6 score is the mean of the responses. Individual changes of ≥ 0.5 are considered to be clinically meaningful, and a decrease from baseline of at least 0.5 is the responder definition for ACQ-6.

From Visit 2 onwards, the participant will complete the ACQ-6 at home every 1 week as per the SoA (Section 1.3 and Section 8.1.5) until the EOT visit. The ePRO device will be set up with functionality to collect unscheduled ACQ-6 assessments on site if required by investigators at a visit.

At each visit, in addition to the information provided by the participant on his/her asthma disease, investigators will have access to the participant's ACQ-6 scores (completed by means of an ePRO) to evaluate whether the participant's condition has not significantly deteriorated (ie, increase in score of ≥ 0.5 from baseline [baseline defined as value at Visit 2 before tezepelumab administration]) and take the final decision to further reduce the OCS dose until the participant reaches the lowest OCS dose possible.

